infiltration, we plan to utilize this dose of R848 two times per week every 3-4 days (+/- 2 days), with the option of dose reducing from twice to once a week should patients experience any grade 3 or greater toxicity.

The physician will designate which of the two regions to receive or not to receive R848. (For example, if the cutaneous disease is limited to the thigh, the area of lesions will be divided in two with one region proximal and one region distal. Then the proximal region is assigned region A and the distal assigned region B. Resiquimod to be applied to region A or B. A 5mm margin will be included in the treatment area around each of the lesions at a spread rate of 10mcg/cm^2. The sum of the area of all treated lesions will not exceed 100cm^2. The treatment area will be allowed to air dry for 30 minutes and then covered with a gauze dressing which can be removed the following day. The R848 gel will be applied in the clinic by the research nurse for the first two weeks of administration, and then the subject will apply the gel at home thereafter. The patient will be trained for gel self-administration by the research staff. Sachets of gel will be supplied for home use and the subject will be instructed on maintaining a home record of administration. This home record or a progress note by one of the research team reviewing home administration may each act as a source document for all matters regarding home administration during this period. The gel may be applied in the clinic for longer than the first two weeks at the discretion of the investigators.

Tumor biopsies of treated and untreated lesions will be obtained as outlined in section 7.3 when feasible in order to assess T-cell infiltration and function at the site.

In order to give patients the opportunity to receive R848 gel on all their lesions, we will allow cross-over of patients who do not respond in untreated lesions by week 16 (8weeks after initiating gel on the tumors) in the untreated lesions to receive R848 gel on all of the lesions, but these patients will not be included in the final analysis of clinical endpoints that occur following week 24. Patients will not cross-over until after all blood, biopsies, and data are recovered for assessment of the primary endpoints in any subject. Treatment with R848 gel will continue for up to 4 months beyond week 24 as long as there is no disease progression.

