## 7.0 Evaluation During Treatment

### 7.1 Clinical Evaluation

Patients will be evaluated every 2 weeks (+/- 2 days) through week 4, then every 4 weeks (+/- 1 week) during the vaccination/treatment. For subjects in the adjuvant cohort, this schedule will continue through week 8, for patients in the metastatic cohort, this will continue until Resiquimod treatment is discontinued. With each patient visit, the evaluation will consist of complete interim history and physical examination, including measurement of vital signs, performance status, and weight. Patients will be evaluated for toxicity and concomitant medications at each visit. Toxicities will be recorded on the toxicity sheet and the medications will be recorded in the patient's electronic medical record. Patients will have a complete blood count (CBC), with differential, PT/PTT, serum electrolytes, BUN, creatinine, glucose, albumin, alkaline phosphatase, ALT, AST, LDH, calcium, and total bilirubin tested at baseline and then tested approximately every 2-4 weeks (using pediatric blood collection tubes if feasible).

For patients in the adjuvant arm,

CT scans of the chest, abdomen, and pelvis will be done at baseline, week 8, (+/- 1 week) and then repeated at 8 week (+/- 1 week) intervals during resiquimod treatment. MRI/CT of the brain will be done at baseline and repeated at the time of the CT scans if clinically indicated.

At discontinuance of vaccination in the adjuvant cohort or resiquimod treatment in the metastatic cohort, clinical follow-up, labs, and staging studies (CT, MRI, PET scans) will be obtained at the discretion of the treating physician following standard clinical pathways.

Subjects in either cohort will be followed on study for 12 months after the completion of therapy (vaccination in the adjuvant cohort, Resiquimod in the metastatic cohort) unless they meet criteria for withdrawal as per section 10.0. Clinical events will be tracked from the physician determined routine clinical follow-up during this period. Clinical events that occur after this period on study may be retroactively recorded from the patient's medical record including tumor progression and death.

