#### **9.5 Immune-Related Best Overall Response Using irRC (irBOR)**

irBOR is the best confirmed irRC overall response over the study as a whole, recorded between the date of first dose until the last tumor assessment before subsequent therapy (except for local palliative radiotherapy for painful bone lesions) for the individual subjects in the study. For assessment of irBOR, all available assessments per subject are considered.

If a lesion is surgically resected or treated with definitive radiosurgery, the size of the lesion prior to the definitive local therapy will be included in the calculated irBOR.

Primary evidence of antineoplastic activity will be evaluated as a function of objective tumor response following the vaccination period. An overall objective assessment of all measurable and non-measurable disease will be performed as outlined in 9.1. Tumor assessments should be performed by physical exam, ultrasound, MRI or CT scan, throughout the study. The treating physicians will perform tumor measurement.

Radiological studies must account for all lesions that were present at baseline and must use the same techniques as used at baseline. All

complete and partial responses must be confirmed by a second assessment at least four weeks later.

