#### **9.6 Baseline measurement**

In this trial a period of immunization opens the treatment, and immunization alone mediates tumor response rarely. (Cancer immunotherapy: moving beyond current vaccines. Rosenberg SA, Yang JC, Restifo NP. *Nat Med.* 2004 Sep;10(9):909-15.) So with this sequence, as has been seen with other immunologic mediators, we should expect that a period of progression may precede any response from the treatment.

Therefore, because subjects are likely to progress during the vaccination portion of the study, the baseline will be that measurement during the first 10 weeks of the study at which the tumors are at their maximum size (based on sum of LD). Progression will be allowed during these first 10 weeks without withdrawal of the subject from treatment or from the study. This includes increase in the size of the lesions as well as the appearance of new lesions.

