## 11.0 Statistical Considerations

### Overview

This is a randomized phase II trial enrolling melanoma patients who are HLA-A2+ with or without HLA-DP4+. Patients of two separate types will be enrolled in separate cohorts. One cohort includes patients who are NED but at high risk for recurrence. The second cohort will include patients with non-visceral metastatic disease and must have at least two evaluable and biopsiable lesions to be eligible for the trial.

The trial will have two parts. In Part 1 (both cohorts), we will fairly randomize patients to receive either the gp100(g209-2M) +/-MAGE3 peptide vaccine plus a topical TLR 7 /8 agonist, R848, (Arm A) or the gp100(g209-2M) +/- MAGE3 vaccine alone Arm B). The randomization will be stratified by cohort. A total of 48 patients will be enrolled, 24 per arm. All patients will receive the gp100(g209-2M) vaccine (those who are HLA-DP4 + will also receive the MAGE3 vaccine) weekly (for 8 weeks) and the patients randomized to receive R848 gel will have the gel applied to the gp100(g209-2M) vaccine site weekly.

After 8 weeks of treatment on Part 1, Part 2 of the trial begins. In Part 2 (only patients in the metastatic disease cohort), the treating physician will divide the area of cutaneous lesions into regions, Region A and Region B and designate the two regions to receive or not to receive R848. At least one lesion will be randomly assigned to receive R848 from weeks 8 through 24, and one will not. One lesion from each region will be chosen for biopsy as outlined in section 7.3. If a patient has more than two evaluable lesions, we will stratify by lesion size to assure that the lesions will be comparable.

As a safety measure, if a patient's untreated lesions grow while treated lesions are stable or shrink, all lesions will be treated with R848. This will occur after the assessment of the primary endpoints of the study, so it will not affect the analysis of these endpoints.

In April 2015, the trial is being further modified to add an additional 20 patients with metastatic disease, all of whom will receive the the gp100(g209-2M) +/-MAGE3 peptide vaccine plus R848 (Arm C). These patients will not be part of the primary comparative study analysis of T-cell responses in the blood. The purpose of these patients is to provide additional information on characterizing tumor response, defined as at least a 50% shrinkage in tumor size by irRC criteria.

### Part 1

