To evaluate the association between clinical response and laboratory parameters of T-cell priming, T-cell migration to tumor, and inflammation at the vaccine and tumor sites we will explore the relationship between immune cell activation measures at the vaccine site (vaccine site measures) and at the tumor site (tumor site measures). Additionally we will assess the effect of the TLR agonist R848 upon clinical response. Clinical response will be assessed using the immune-related response criteria (irRC) and will be assessed at week 8, 16, and every 8 weeks thereafter. Since both vaccine site measures and tumor site measures are continuous variables we will assess association between these two types of variables using Pearson's or Spearman's correlation coefficient. In addition, we will use logistic regression to model the relationship between either vaccine site or tumor measures and best clinical response assessed over a 16 weeks period after initial vaccination.

To assess the association between R848 treatment on lesions and response, the irRC will be used to assess response separately by lesion type (lesions receiving or not receiving R848 cream). That is, using the irRC, we will, for each patient, assess if the lesions not treated with R848 cream responded and also determine if the lesions treated with R848 cream responded. Thus, for each patient we will record 4 possible joint outcomes ++, +-, -+, and --, where the ++ indicates that both lesions receiving and not receiving R848 cream responded; -- indicates neither types of lesions responded. Similarly +- and -+ indicate one type of lesion responded while the other did not. We will assess differences between treatments (based on within patient differences) using McNemar's test. A statistically significant difference with respect to the McNemar's test will indicate if cream administered to the lesion results in improved outcome (i.e., immune-related response criteria) relative to lesions for which cream was not administered.

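### Read literally, the 16-week window for best clinical response holds one scheduled post-gel assessment and no time to confirm it, so later responders count as non-responders.

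*Combined protocol and SAP*

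**What the plan says.** - **Outcome of the association model.** Section 11.0, Overview of Analysis of Secondary Endpoints, takes "best clinical response assessed over a 16 weeks period after initial vaccination" as the dependent variable of a logistic regression on vaccine-site or tumour-site measures.
- **Assessment times.** The same paragraph says that clinical response "will be assessed at week 8, 16, and every 8 weeks thereafter". Section 7.1 has CT scans at baseline and week 8, "then repeated at 8 week (+/- 1 week) intervals during resiquimod treatment". That sentence sits under a line about the adjuvant arm, but gel on tumours applies only to the metastatic cohort.
- **Gel on tumours.** The Section 11.0 Overview dates it: "At least one lesion will be randomly assigned to receive R848 from weeks 8 through 24". Section 6.0 adds: "Treatment with R848 gel will continue for up to 4 months beyond week 24", provided there is no progression.
- **Confirmation.** Section 9.5 says that all "complete and partial responses must be confirmed by a second assessment at least four weeks later". It defines immune-related best overall response (irBOR) as a confirmed response, taken over the entire trial and from every available assessment.
- **Baseline.** Section 9.6 says "the baseline will be that measurement during the first 10 weeks of the study" with the largest tumour size. It gives the reason: growth may come before any response.
- **Crossover.** Section 6.0 lets patients whose untreated lesions have not responded by week 16 receive gel on all lesions. It drops these patients from the analysis of clinical endpoints arising after week 24.

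**The concern.** The window runs from the first vaccination, but the treatment expected to shrink tumours starts half-way through it. The outcome is therefore fixed after eight weeks of gel, while gel is planned for sixteen weeks and may continue for up to four months more. Section 9.6 expects responses to come late, and Section 9.5 counts them whenever they come. The association model does neither.

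This is the only model in the plan that relates clinical response to the laboratory measures, so this part of objective C (Section 1.2) depends on it. The number of events limits what a logistic model can show, and a short window costs events. The plan also does not say whether a response seen at week 16 and not yet confirmed counts as a response.

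**Working it through.** **Inputs.** Gel start: week 8 (Sections 6.0 and 11.0). irRC grid: weeks 8, 16, 24, 32 and so on (Section 11.0). Scan allowance: 1 week either way (Section 7.1). Confirmation: at least 4 weeks later (Section 9.5). Window end, read literally: week 16.

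**Step 1: the plan's own timing.** Section 6.0 refers to "week 16 (8weeks after initiating gel on the tumors". 16 − 8 = 8 weeks, so gel start at week 8 is reproduced.

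**Step 2: earliest confirmation of a post-gel response.** The first post-gel assessment is at week 16. By rule, 16 + 4 = week 20; on the grid, the next assessment is week 24. That is 4 to 8 weeks after the window closes. Using the scan allowance, 15 + 4 = week 19, still later than 16 + 1 = week 17.

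**Step 3: pairs (first seen, confirmed) that fit inside the window.**

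| Window ends | Grid | Post-gel assessments inside | Pairs inside |
|---|---|---|---|
| Week 16 | Planned irRC, 8-weekly | 16 | none |
| Week 16 | Exam at 4-weekly visits | 12, 16 | (12, 16) |
| Week 24 | Planned irRC, 8-weekly | 16, 24 | (16, 24) |
| Week 24 | Exam at 4-weekly visits | 12, 16, 20, 24 | (12, 16), (12, 20), (12, 24), (16, 20), (16, 24), (20, 24) |

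On the planned grid, the only response that can be seen and confirmed by week 16 is one first seen at week 8, before gel. Section 2.4 puts vaccine response under 3%. In the 20 Part 2 patients first planned, that is fewer than 0.03 × 20 = 0.6 patients.

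**Step 4: baseline.** If tumour size peaks at week 10, a 50% shrinkage must be reached in 16 − 10 = 6 weeks to be seen by week 16.

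**Step 5: how many events are lost.** No response rate is stated for this model. As an illustration only, take the 22% alternative of the Arm A plus C test: 0.22 × 20 = 4.4 or 0.22 × 30 = 6.6 responders.
- If confirmation must fall inside the window, all of those first responding after gel start are coded as non-responders on the planned grid.
- If later confirmation is accepted, only those first responding at week 24 or later are miscoded. That share is not given (0 to 100%).

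**Step 6: direction of bias.** Assume true response of 30% against 14% in patients high and low on a marker. The odds ratio is (0.30/0.70) / (0.14/0.86) = 2.63.
- Half of responders missed in both groups: (0.15/0.85) / (0.07/0.93) = 2.34.
- Half missed in the low group only, as when strong priming speeds response: (0.30/0.70) / (0.07/0.93) = 5.69.
- Half missed in the high group only: (0.15/0.85) / (0.14/0.86) = 1.08.

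The sign depends on how marker level relates to speed of response, which the documents do not address.

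**The case against.** **The window may mean weeks 8 to 24.** Section 7.3 speaks of the first vaccination when it means the first dose, Section 9.6 describes immunization as an opening period, and gel from week 8 through 24 lasts exactly 16 weeks. This reading is possible. Counting from the first injection is still the plainer one, and a plan should not leave an outcome window open to both. If weeks 8 to 24 were meant, the fix only makes that explicit.

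**A reader might infer that no post-gel response can ever be confirmed by week 16.** The documents do not support that. Section 7.1 has clinic visits at weeks 12 and 16, Section 9.5 accepts physical examination, and Sections 9.1 and 9.2 allow small skin lesions as measurable and expect many patients to have only those. A response measured at week 12 could be confirmed at week 16. Week 12 is not on the irRC grid of Section 11.0, however, and this route catches only very early responders.

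**A reader might also infer that the model has no events.** That needs confirmation to fall inside the window, which Section 11.0 does not say. If later confirmation is accepted, week-16 responders are kept. The loss of those first responding at week 24 or later remains.

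**Week 16 has a rationale.** Crossover becomes possible then, so a week-16 cut gives everyone the same follow-up before crossover. This stands, and it is why the week-16 outcome should be kept as a sensitivity analysis.

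**The analysis is exploratory and secondary.** This is true, and it limits how much the point matters.

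**Conclusion.** The point holds for the literal window and the planned irRC grid. There is one scheduled post-gel assessment, no post-gel response both seen and confirmed inside the window, and non-response coding for anyone first responding at week 24 or later. That conflicts with the whole-trial irBOR of Section 9.5 and with the late responses that Section 9.6 expects.

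The established cost is lost events and precision in the objective C model, of a size that the documents do not let one state. Two stronger conclusions are tempting and not supported. One is that the association is pulled toward zero: the bias could go either way. The other is that six or seven responders are lost: 22% of 30 is the power alternative for Arms A and C, not an expected count for this model, which may also draw on Arm B and, for tumour-site measures, depends on optional biopsies.

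The Part 1 comparison, the Arm A plus C response test and the McNemar analysis carry no 16-week cut and are unaffected.

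**What to change.** In Section 11.0, define the outcome of the logistic model as best irRC response from week 8 through week 24 for every metastatic-cohort patient in the model. Allow the confirming assessment to fall after week 24, and state that unconfirmed responses count as non-response. Say that this confirmation belongs to the week-24 outcome, so that it does not clash with Section 6.0's exclusion of crossed-over patients from later endpoints.

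Apply the same window to all patients; do not stop follow-up at crossover. Crossover depends on non-response by week 16. Cutting there would leave patients who cross at that point with one post-gel assessment (week 16) and the others with two (weeks 16 and 24), so follow-up would depend on outcome. Report the week-16, pre-crossover outcome as a sensitivity analysis.

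Exact or Firth logistic regression is optional if events are few.

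The cost is a change of analysis wording; week 24 is already on the irRC schedule. The small downside is that some week-24 assessments may follow crossover to gel on all lesions, which the sensitivity analysis addresses.

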## Study Stopping Criteria

We will conduct an interim analysis after half of the patients have been enrolled and have reached week 8 on the study. At the interim analysis, we will test whether there is strong evidence that the immune responses differ between the two treatment arms. We will use an O'Brien-Fleming stopping boundary to stop for efficacy, with a nominal significance level of 0.0056. With the alpha spent at the interim look, the nominal significance level at the final analysis will be 0.0482.

## 12.0 Data Entry and Protocol Management

For the purposes of this study at M. D. Anderson Cancer Center, the Protocol Data Management System (PDMS) will be employed. All patients will be registered in PDMS/CORE. This study will be monitored by the MDACC Compliance Office. The randomization will be done by the CORE system and the data will be reviewed annually by the institution's Data Safety Monitoring Board (DSMB). The statisticians will prepare the report for review by the DSMB.

## 13.0 Administrative Procedures

### 13.1 Changes to the protocol:

Any change or addition to this protocol requires a written protocol amendment that must be approved by the IRB. A copy of the written approval of the IRB must be received before implementation of any changes. The IRB must review and approve all amendments to the protocol.

### 13.2 Ethics and good clinical practice:

This study must be carried out in compliance with the protocol and Good Clinical Practice, as described in:

**13.2.1.1.1** ICH Harmonized Tripartite Guidelines for Good Clinical Practice 1996.

**13.2.1.1.2** US 21 Code of Federal Regulations dealing with clinical studies (including parts 50 and 56 concerning informed consent and IRB regulations).

**13.2.1.1.3** Declaration of Helsinki, concerning medical research in humans (Recommendations Guiding Physicians in Biomedical Research Involving Human Subjects, Helsinki 1964, amended Tokyo 1975, Venice 1983, Hong Kong 1989, Somerset West 1996). The investigator agrees, when signing the protocol, to adhere to the instructions and procedures described in it and thereby to adhere to the principles of Good Clinical Practice.

